8.4.2 Electrocardiogram

At the Screening Visit, an ECG must be recorded after 10 minutes rest in the supine position to ensure a stable baseline. The preferred sequence of cardiovascular data collection at is ECG first, followed by vital signs, and blood sampling for laboratory assessments. The Fridericia QT correction formula (QTcF) should be used for clinical decisions.

If the ECG findings are clinically relevant and would prevent the subject from participating in the study (taking into account the subject's overall status and the medication profile), the subject should be recorded as a screen failure, should not be enrolled and should not receive treatment.

Single 12-lead ECGs will be collected. The original ECGs, appropriately signed, should be collected and archived at the study site.

Each ECG tracing must be labelled with study number, subject initials, subject number, date and time, and filed in the study site source documents. Clinically significant ECG findings at Baseline must be discussed with the Sponsor before administration of study treatment.

For any ECGs with subject safety concerns, 2 additional ECGs must be performed to confirm the safety finding and copies forwarded to the central ECG laboratory for assessment. A monitoring or review process should be in place for clinically significant ECG findings throughout the study and especially at Baseline before administration of study treatment.

Any identifier details must be redacted e.g., subject initials, date of birth.

In the event that a clinically significant ECG abnormality is identified at the site (e.g., severe arrhythmia, conduction abnormality of QTcF > 500 ms), a copy of the assessment is sent to the core laboratory for expedited review if applicable, and the ECG is repeated to confirm the diagnosis. If the subject is hemodynamically compromised, the Investigator or a medically qualified person must initiate appropriate safety procedures without delay (for example cardioversion).

Clinically significant abnormalities must be recorded on the eCRF as either medical history/current medical conditions or AEs as appropriate.

8.4.3 Pregnancy

All pre-menopausal women who are not surgically sterile will have pregnancy testing. Additional pregnancy testing might be performed if requested by local requirements.

Medical documentation of oophorectomy, hysterectomy, or tubal ligation must be retained as source documents. Subsequent hormone level assessment to confirm the woman is not of childbearing potential must also be available as source documentation in the following cases:

1. Surgical bilateral oophorectomy without a hysterectomy
2. Reported 12 months of natural (spontaneous) amenorrhea with an appropriate clinical profile

[figure not shown]
[figure not shown]
In the absence of the above medical documentation, follicle-stimulating hormone testing is required of any female subject, regardless of reported reproductive/menopausal status at Screening/Baseline.

8.4.4 Appropriateness of safety measurements

The safety assessments selected are standard for this indication/subject population.

8.5 Additional assessments

9 Study discontinuation and completion

9.1 Discontinuation

9.1.1 Discontinuation of study treatment

Discontinuation of study treatment for a subject occurs when study treatment is stopped earlier than the protocol planned duration, and can be initiated by either the subject or the Investigator.

The Investigator must discontinue study treatment for a given subject if, he/she believes that continuation would negatively impact the subject's well-being.

Study treatment must be discontinued under the following circumstances:

- subject decision
- pregnancy
- use of prohibited treatment as per recommendations in the prohibited treatment section
- any situation in which study participation might result in a safety risk to the subject
- any laboratory abnormalities that in the judgment of the Investigator, taking into consideration the subject's overall status, prevents the subject from continuing participation in the study

If discontinuation of study treatment occurs, the Investigator should make a reasonable effort to understand the primary reason for the subject's premature discontinuation of study treatment and record this information.

Subjects who discontinue study treatment or who decide they do not wish to participate in the study further should NOT be considered withdrawn from the study UNLESS they withdraw their consent (see [Section 9.1.2](#)). **Where possible, they should return for the assessments indicated** in the assessment schedule. If they fail to return for these assessments for unknown reasons, every effort (e.g., telephone, e-mail, or letter) should be made to contact the subject/pre-designated contact as specified in the lost to follow-up section. This contact should preferably be done according to the study visit schedule.

If the subject cannot or is unwilling to attend any visit(s), the site staff should maintain regular telephone contact with the subject, or with a person pre-designated by the subject. This telephone contact should preferably be done according to the study visit schedule.

After study treatment discontinuation, at a minimum, in abbreviated visits, the following data should be collected at study site visits or via telephone/email contact:

- new/concomitant treatments
- adverse events/SAEs

The Investigator must also contact the NIRT to register the subject's discontinuation from study treatment.

9.1.2 Withdrawal of informed consent

Subjects may voluntarily withdraw consent to participate in the study for any reason at any time. Withdrawal of consent occurs only when a subject:

- does not want to participate in the study anymore

and

- does not allow further collection of personal data

In this situation, the Investigator should make a reasonable effort (e.g., telephone, e-mail, or letter) to understand the primary reason for the subject's decision to withdraw his/her consent and record this information.

Study treatment must be discontinued and no further assessments conducted, and the data that would have been collected at subsequent visits will be considered missing.

Further attempts to contact the subject are not allowed unless safety findings require communicating or follow up.

All efforts should be made to complete the assessments prior to study withdrawal. A final evaluation at the time of the subject's study withdrawal should be made as detailed in the assessment table.

Novartis will continue to retain and use collected study information (including any data resulting from the analysis of subject's samples until the time of withdrawal) according to applicable law.

For US and Japan: all biological samples not yet analyzed at the time of withdrawal may still be used for further testing/analysis in accordance with the terms of this protocol and of the informed consent form.

For EU and rest of the world: all biological samples not yet analyzed at the time of withdrawal will no longer be used unless permitted by applicable law. They will be stored according to applicable legal requirements.

9.1.3 Lost to follow up

For subjects whose status is unclear because they fail to appear for study visits without stating an intention to discontinue or withdraw, the Investigator must show “due diligence” by documenting in the source documents steps taken to contact the subject, e.g., dates of telephone calls, registered letters, etc. A subject should not be considered as lost to follow up until due diligence has been completed or until the end of the study.

9.1.4 Early study termination by the Sponsor

The study can be terminated by Novartis at any time for any reason. This may include reasons related to the benefit/risk assessment of participating in the study, practical reasons (including slow enrollment), or for regulatory or medical reasons. In taking the decision to terminate, Novartis will always consider the subject welfare and safety. Should early termination be necessary, subjects must be seen as soon as possible (provide instruction for contacting the subject, when the subject should stop taking drug, when the subject should come for a final visit) and treated as a prematurely withdrawn subject. The Investigator may be informed of additional procedures to be followed in order to ensure that adequate consideration is given to the protection of the subject’s interests. The Investigator or sponsor depending on the local regulation will be responsible for informing IRBs/IECs of the early termination of the study.

9.2 Study completion and post-study treatment

Study completion is defined as when the last subject finishes their End-of-study Visit, and any repeat assessments associated with this visit have been documented and followed up appropriately by the Investigator, or in the event of an early study termination decision, the date of that decision (e.g., each subject will be required to complete the study in its entirety and thereafter no further study treatment will be made available to them).

All randomized and/or treated subjects should have a safety follow up conducted 30 days after the last administration of study treatment. This will be performed at Week 16 for subjects who complete the study [last administration received at Week 12]. The information collected is kept as source documentation. All SAEs reported during this period must be reported as described in [Section 10.1.3](#). Attempts to contact the subject should be recorded in the source documentation.

10 Safety monitoring and reporting

10.1 Definition of adverse events and reporting requirements

10.1.1 Adverse events

An AE is any untoward medical occurrence (e.g., any unfavorable and unintended sign [including abnormal laboratory findings], symptom or disease) in a subject or clinical investigation subject after providing written informed consent for participation in the study. Therefore, an AE may or may not be temporally or causally associated with the use of a medicinal (investigational) product.

The Investigator has the responsibility for managing the safety of individual subject and identifying AEs.

Novartis qualified medical personnel will be readily available to advise on study related medical questions or problems.

The occurrence of AEs must be sought by non-directive questioning of the subject at each visit during the study. Adverse events also may be detected when they are volunteered by the subject during or between visits or through physical examination findings, laboratory test findings, or other assessments.

Adverse events must be recorded under the signs, symptoms or diagnosis associated with them, accompanied by the following information (as far as possible, if the event is serious refer to [Section 10.1.2](#)):

1. The Common Toxicity Criteria (CTC) AE grade (version 4.03 or higher). Adverse events will be assessed and graded according to the Common Terminology Criteria for Adverse Events (CTCAE) version
2. Its relationship to the study treatment. If the event is due to lack of efficacy or progression of underlying illness (i.e., progression of the study indication) the assessment of causality will usually be 'Not suspected'. The rationale for this guidance is that the symptoms of a lack of efficacy or progression of underlying illness are not caused by the trial drug, they happen in spite of its administration and/or both lack of efficacy and progression of underlying disease can only be evaluated meaningfully by an analysis of cohorts, not on a single subject
3. Its duration (start and end dates) or if the event is ongoing, an outcome of not recovered/not resolved must be reported.
4. Whether it constitutes a SAE (see [Section 10.1.2](#)) for definition of SAE) and which seriousness criteria have been met
5. Action taken regarding with study treatment.

All AEs must be treated appropriately. Treatment may include one or more of the following:

- dose not changed
 - dose reduced/increased
 - drug interrupted/withdrawn
6. Its outcome, i.e., its recovery status or whether it was fatal

Conditions that were already present at the time of informed consent should be recorded in medical history of the subject.

Adverse events (including laboratory abnormalities that constitute AEs) should be described using a diagnosis whenever possible, rather than individual underlying signs and symptoms.

Adverse event monitoring should be continued for at least 30 days following the last dose of study treatment.

Information about adverse drug reactions for the investigational drug can be found in the IB.

Abnormal laboratory values or test results constitute AEs only if they fulfill at least one of the following criteria:

- they induce clinical signs or symptoms
- they are considered clinically significant
- they require therapy

Clinically significant abnormal laboratory values or test results must be identified through a review of values outside of normal ranges/clinically notable ranges, significant changes from Baseline or the previous visit, or values that are considered to be non-typical in subjects with the underlying disease.

10.1.2 Serious adverse events

An SAE is defined as any AE (appearance of or worsening of any pre-existing one) undesirable sign, symptom or medical conditions that meets any one of the following criteria:

- fatal
- life-threatening

Life-threatening in the context of a SAE refers to a reaction in which the subject is at risk of death at the time of the reaction; it does not refer to a reaction that hypothetically might have caused death if it were more severe (please refer to the ICH-E2D Guidelines).

- results in persistent or significant disability/incapacity
- constitutes a congenital anomaly/birth defect
- requires inpatient hospitalization or prolongation of existing hospitalization, unless hospitalization is for:
 - a. routine treatment or monitoring of the studied indication, not associated with any deterioration in condition (including psoriasis and psoriatic arthritis)
 - b. elective or pre-planned treatment for a pre-existing condition that is unrelated to the indication under study and has not worsened since signing the informed consent
 - c. social reasons and respite care in the absence of any deterioration in the subject's general condition
 - d. treatment on an emergency outpatient basis for an event not fulfilling any of the definitions of a SAE given above and not resulting in hospital admission
- is medically significant, e.g., defined as an event that jeopardizes the subject or may require medical or surgical intervention to prevent one of the outcomes listed above

Medical and scientific judgment should be exercised in deciding whether other situations should be considered serious reactions, such as important medical events that might not be immediately life threatening or result in death or hospitalization but might jeopardize the subject or might require intervention to prevent one of the other outcomes listed above. Such events should be considered as “medically significant”. Examples of such events are intensive treatment in an emergency room or at home for allergic bronchospasm, blood dyscrasias or convulsions that do not result in hospitalization or development of dependency or abuse.

All malignant neoplasms will be assessed as serious under “medically significant” if other seriousness criteria are not met.

Any suspected transmission via a medicinal product of an infectious agent is also considered a serious adverse reaction.

All reports of intentional misuse and abuse of the product are also considered SAEs irrespective if a clinical event has occurred.

10.1.3 Serious adverse event reporting

To ensure subject safety, every SAE, regardless of causality, occurring after the subject has provided informed consent and until 30 days following the last administration of study treatment must be reported to Novartis Safety within 24 hours of learning of its occurrence. Detailed instructions regarding the submission process and requirements are to be found in the Investigator folder provided to each study site.

Serious adverse events occurring after the subject has provided informed consent until the time the subject is deemed a Screen Failure must be reported to Novartis.

All follow-up information for the SAE including information on complications, progression of the initial SAE and recurrent episodes must be reported as follow up of the original episode within 24 hours of the Investigator receiving the follow-up information. An SAE occurring at a different time interval or otherwise considered completely unrelated to a previously reported one must be reported separately as a new event.

If the SAE is not previously documented in the IB or Package Insert (new occurrence) and is thought to be related to the study treatment, an associate from the Novartis Chief Medical Office and Patient Safety (CMO&PS) Department may urgently require further information from the Investigator for health authority reporting. Novartis may need to issue an Investigator Notification (IN) to inform all Investigators involved in any study with the same study treatment that this SAE has been reported.

Suspected unexpected serious adverse reactions (SUSARs) will be collected and reported to the competent authorities and relevant ethics committees in accordance with EU Guidance 2011/C 172/01 or as per national regulatory requirements in participating countries.

Any SAEs experienced after the 30-day period following the last administration of study treatment should only be reported to Novartis Safety if the Investigator suspects a causal relationship to study treatment.

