4.5.1.3 Risks associated with the skin biopsy procedure

A skin biopsy is a routine procedure as part of the diagnostic practice in all dermatology clinics, which may cause bleeding and infections. Subjects may experience bruising, swelling, pain in the area, scarring and fainting caused by a drop in blood pressure. They may also have an allergic response from the anesthetic agent used for the procedure.

Wound healing after the procedure may be compromised in subjects who are smokers or take steroids.

[REDACTED]

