6.7.2 Instruction for prescribing and taking study treatment

Study treatments will be administered subcutaneously throughout the study (Table 6-3). The first dose will be administered under supervision at the study site. Self-administration at home will be allowed from the second dose or when the subject, after being instructed and trained, is qualified to self-inject at the discretion of the Investigator.

Study treatments must be injected in never-lesional areas of the skin to one of the following body regions: front of thighs, or lower abdomen (but not the area 2 centimeters around the navel). Investigator/qualified site staff can also inject in the outer upper arms. Study treatment should not be injected into areas where the skin is tender, bruised, red, scaly or hard, and areas with scars or stretch marks should be avoided. As far as possible, the injection site should be changed from administration to administration throughout the study.

Detailed instructions on the self-administration of the study treatment will be described in the instructions for use and provided to each subject.

Subjects will be asked to return all used and unused medication and packaging at each scheduled study visit.

Secukinumab 300 mg s.c.

Secukinumab will be administered at Baseline, Weeks 1, 2, 3, 4 and then every 4 weeks until Week 12 inclusive. After Week 4 (the last weekly administration of secukinumab), the subjects will be contacted by the Investigator or staff and be reminded to start the self-administration every 4 weeks instead of every week until Week 12.

Guselkumab 100 mg s.c.

Guselkumab will be administered subcutaneously at Baseline, Weeks 4, and 12.

Table 6-3 Study treatment administration schedule

Treatment	Baseline	Week 1	Week 2	Week 3	Week 4	Week 8	Week 12
Secukinumab	X	X	X	X	X	X	X
Guselkumab	X				X		X

7 Informed consent procedures

Eligible subjects may only be included in the study after providing (witnessed, where required by law or regulation), Institutional Review Board/Independent Ethics Committee (IRB/IEC)-approved informed consent.

If applicable, in cases where the subject's representative gives consent (if allowed according to local requirements), the subjects must be informed about the study to the extent possible given their understanding. If the subjects are capable of doing so, they must indicate agreement by personally signing and dating the written informed consent document.

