Subjects should be seen for all visits/assessments as outlined in the assessment schedule or as close to the designated day/time as possible. Missed or rescheduled visits should not lead to automatic discontinuation. Subjects who prematurely discontinue the study for any reason should be scheduled for a visit as soon as possible, at which time all of the assessments listed for the final visit will be performed. At this final visit, all dispensed investigational product should be reconciled, and the AEs and concomitant medications recorded on the eCRF.

[REDACTED]

Table 8-1 Assessment schedule

Visit name	Screening	Baseline	End of study	Unscheduled
Visit number	1	2	3	-
Week	-4 to -1	-	16	-
Day	-28 to -1	1	112	-
Informed consent	X			
Inclusion/exclusion criteria	X	X		
Pregnancy test ²	X	X		
Randomization via NIRT		X		
Physical examination	X	X	X	X
Smoking history	X			
Medical history	X			
Relevant family history	X			
Demography	X			
Psoriasis medical and treatment history	X			
QFT	X			
Skin type	X			
Body temperature (°C)	X	X		
Height (cm)	X			
Weight (Kg)	X	X	X	
Vital signs	X	X	X	
Electrocardiogram	X			
Laboratory assessments	X		X	
Adverse events ³	X	X	X	X
Drug administration record		X	X	X
Concomitant medications	X	X	X	X
TCS of target plaque	X	X	X	X
Skin biopsies ██████████ ⁶		X	X	
Information on study completion			X	

Baseline Visit (Visit 2) should be conducted within 28 days of the Screening Visit (Visit 1).

Unscheduled visits can be decided by the Investigators according to their own clinical judgment and practice.

End-of-study assessments (Visit 3) should be conducted only on subjects who complete 4 to 16 weeks of treatment. There will be a \pm 2-day window for Visit 3 (Week 16)

- [REDACTED]
- 2) Performed on serum for women of childbearing potential
 - 3) SAEs collected up to 30 days after the last administration of study treatment

[REDACTED]

6) At Baseline, two 6-mm punch biopsies will be taken, one from the identified active plaque (TCS \geq 6) and one from never-lesional skin. At the End-of-study Visit, one biopsy will be taken from the same area of the plaque sampled at Baseline. Biopsies should be sampled from the trunk whenever possible to avoid scars in exposed areas of the body

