8.3.3 Skin biopsies

At Baseline, two 6-mm punch biopsies will be taken, one from the identified active plaque (TCS \geq 6) and one from never-lesional skin. At the End-of-study Visit, one biopsy will be taken from the same area of the active plaque sampled at Baseline.

After collection, biopsies will be transported within 24 hours to the laboratory for further processing using a Novartis delegated service provider.

Laboratory manuals will be provided with detailed information on sample collection, handling, and shipment. The sample collection date and exact time must be entered on the Sample Collection eCRF page.

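### After the final plaque biopsy a completer has only 0 to 4 days of the SAE window left, and a later SAE attributed solely to the biopsy falls outside the reporting rule

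*Protocol*

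**What the plan says.** **The procedure.** Section 4.5.1.3 describes skin biopsy as a procedure "which may cause bleeding and infections", and also lists swelling, pain and scarring. Section 8.3.3 fixes the last one: "At the End-of-study Visit, one biopsy will be taken from the same area of the active plaque sampled at Baseline". Table 8-1 puts that visit at Week 16, Day 112, with a window of 2 days either side, and schedules nothing after it.

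**The clock.** Section 10.1.1 states: "Adverse event monitoring should be continued for at least 30 days following the last dose of study treatment". A note to Table 8-1 ends SAE collection 30 days after the last administration. Section 10.1.3 uses the same limit for mandatory SAE reporting, and Section 12.7 uses it for the safety tables. None of these refers to the biopsy.

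**After the clock stops.** Under Section 10.1.3 a later SAE "should only be reported to Novartis Safety if the Investigator suspects a causal relationship to study treatment". Table 6-1 and Section 6.1.2 limit study treatment to secukinumab and guselkumab, whereas the glossary entry covers a drug or an intervention. Section 10.1.1 asks for causality against study treatment only.

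**The last contact.** Section 9.2 gives every randomized or treated subject a safety follow-up 30 days after the last dose, but for completers it is carried out at the Week 16 visit itself. The same section states: "Study completion is defined as when the last subject finishes their End-of-study Visit".

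**Dosing.** For the secukinumab arm: "Secukinumab will be administered at Baseline, Weeks 1, 2, 3, 4 and then every 4 weeks until Week 12 inclusive". For the guselkumab arm: "Guselkumab will be administered subcutaneously at Baseline, Weeks 4, and 12".

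**The concern.** The last invasive procedure required by the protocol coincides with the last planned contact, and every safety window is tied to the drug. Wound infection and delayed bleeding appear after a biopsy, not during it. If the window is nearly or already closed on that day, a serious complication depends on the late-reporting rule, and that rule asks only about the drugs.

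An SAE that the investigator attributes to the biopsy alone would then not have to go to the sponsor's safety department. Sites could also differ, because the glossary and Section 6.1 disagree on whether a biopsy can count as study treatment. The biopsy serves only exploratory endpoints, so a full account of its harms matters for the subjects who agree to it.

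**Working it through.** **Inputs.** Week 16 = Day 112 (Table 8-1), so a week converts as day = 7 x week and Week 12 = Day 84. Because Baseline is Day 1, Week 12 could also be read as Day 85; both readings are shown. The biopsy falls on Days 110 to 114. The window is 30 days from the last dose.

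**The plan's own figure.** Section 9.2 says the 30-day follow-up after the Week 12 dose is met at Week 16.
- Week 12 = Day 84: 112 - 84 = 28 days; with the visit window, 110 - 84 = 26 to 114 - 84 = 30.
- Week 12 = Day 85: 112 - 85 = 27 days; with the visit window, 25 to 29.

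The stated 30 days is therefore reached only on the last permitted day, or never on the second reading. Section 10.1.1 sets 30 days as a minimum, so the two sections do not agree.

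**Completers dosed on schedule.** Days left = (last dose day + 30) - biopsy day.

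| Week 12 dose | Window ends | Biopsy Day 110 | Day 112 | Day 114 |
|---|---|---|---|---|
| Day 84 | Day 114 | 4 | 2 | 0 |
| Day 85 | Day 115 | 5 | 3 | 1 |

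**Treatment stopped early, subject returns at Week 16.** Section 9.1.1 asks such subjects to return for the scheduled assessments where possible. With Week w = Day 7w:
- Secukinumab, last dose Week 8: 56 + 30 = Day 86. The window closed 110 - 86 = 24 to 114 - 86 = 28 days before the biopsy.
- Guselkumab, last dose Week 4: 28 + 30 = Day 58. The window closed 110 - 58 = 52 to 114 - 58 = 56 days before it.

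**Early exit with an exit biopsy, all doses due so far taken.**
- Guselkumab, last dose Day 28, next dose due Day 84: an exit on Days 59 to 83 falls 59 - 58 = 1 to 83 - 58 = 25 days after closure.
- Secukinumab from Week 4: doses are 28 days apart, which is less than 30, so the window is still open at any exit day up to Day 112.
- Either arm, last dose Day 28, final visit Day 35: 58 - 35 = 23 days remain. The maximum is 30, when the final visit is on a dosing day.

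So a closed window on early exit without a missed dose arises only in the guselkumab arm, because of its 8-week dosing gap.

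**What the rule then does.** Inside the window every SAE is reportable whatever its cause. Outside it, the test is a suspected link to study treatment. Under Section 6.1 a biopsy is not study treatment, so a purely procedural SAE fails the test. Under the glossary it might pass.

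**The case against.** A 30-day window counted from the last dose, used consistently in four places, is a legitimate design, and much of the protocol limits the gap. A reader might draw three stronger conclusions that the text does not support.

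- **That biopsy risks in general go unfollowed.** Each subject has two Baseline biopsies and one final one, so with 40 subjects 2 x 40 = 80 of at most 3 x 40 = 120 biopsies are taken at Baseline. Adverse events are collected from consent, so completers' Baseline biopsies have about 16 weeks of follow-up. The trial can describe the safety of its procedure. Early stoppers seen soon after a dose keep up to 30 days, and the Section 9.2 follow-up can then come after their exit biopsy.
- **That sites are told not to record late complications.** Section 10.1.1 sets a minimum for monitoring, not a cap. The restriction in Section 10.1.3 concerns late SAE reporting only. Unscheduled visits are open to the investigator and include adverse event collection.
- **That any serious wound infection is lost.** Infection is a named risk of secukinumab, and certain infections are listed for guselkumab. An investigator who suspects the drug must still report, with no time limit. What is excluded is a late SAE judged purely procedural.

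It is also fair that 6 mm is stated only for the Baseline biopsies, that impaired healing is named only for smokers and steroid users, and that end-of-study assessments are limited to subjects with 4 to 16 weeks of treatment.

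These points narrow the finding but do not remove it. Permission to monitor for longer schedules no contact after the final biopsy, and the late-reporting criterion still omits the procedure.

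**Conclusion.** The point stands for final biopsies in two groups. Completers dosed on schedule have 0 to 4 days of window left (1 to 5 if Week 12 is Day 85) and no scheduled contact in that time. Subjects last dosed more than 30 days before the final visit have none, for example a guselkumab subject last dosed at Week 4 who exits on Days 59 to 83. At most 40 final biopsies are involved, and the documents give no basis for estimating how many serious complications would follow.

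The figures assume home doses taken on the scheduled day. The protocol states no dosing window, and a late Week 12 dose would lengthen the cover. The exclusion of a purely procedural SAE assumes the Section 6.1 meaning of study treatment.

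Separately, Section 9.2 contradicts its own figure: 28 days is presented as a 30-day follow-up. The point is modest, does not touch the primary analysis, and is cheap to correct.

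**What to change.** 1. In Section 10.1.3, extend the criterion for SAEs after the 30-day period to a suspected causal relationship to study treatment or a study procedure.
2. In Section 10.1.1, record relatedness to a study procedure alongside relatedness to the drug. In Section 12.7, list procedure-related events separately from drug-related treatment-emergent events.
3. Reconcile the glossary entry for study treatment, Section 6.1.2, the notes to Table 8-1, and Sections 9.2, 10.1.1 and 10.1.3, so that they agree on whether event collection covers the final biopsy and on whether Week 16 meets the 30-day follow-up. The sponsor should set any interval; the documents give no basis for choosing one here.

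The cost is amendment wording and one eCRF field. If the sponsor chooses to extend collection past the final biopsy, the extra contacts would be a further cost.
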